4.0 Study Endpoints*

Pulmonary function as measured by:

- PFTs: FEV1, FEV1%, FVC, FVC%

Inflammation as measured by:

- Blood Eosinophils, Neutrophil, CRP

Quality of life as measured by:

- Dyspnea scores (31): Borg
- HRQOL
 - St George's Respiratory Questionnaire
 - PH Q9
- 6-minute walk distance

PROTOCOL TITLE: Exploring the Dose-Response Effect of Adjunctive Acupuncture on Pulmonary Rehabilitation: A Pilot Study

- The incidence of Acute Exacerbations (AE)

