6.0 Procedures Involved*

The study will use a wait-time control design with varying intervention durations, i.e., dose.

Group	
A	INTERVENTION- 8 weeks acupuncture
B	INTERVENTION- 4 week acupuncture
C	SOC CONTROL- standard of care for the study duration

PROTOCOL TITLE: Exploring the Dose-Response Effect of Adjunctive Acupuncture on Pulmonary Rehabilitation: A Pilot Study

Patients will be recruited from the DHMC pulmonary rehab program. They will be randomized to start in group A or B with groups A and B to the EA intervention of 4 or 8 weeks or will volunteer to be a control subject in group C.

Current practice at the DHMC pulmonary rehabilitation unit is 6 - 12 patient per rehab cohort. Their program is applied in 4- or 8- week increments.

As this is a pilot, part of the study is to evaluate the facilitators and barriers to recruitment. For example, this protocol can be extended in time if recruitment is slow. We will be aiming for at least 10 participants per arm. If recruitment is robust, we will cap each arm at 30 participants.

Intervention: DHMC pulmonary rehabilitation program + EA Lung Mu-Shu+ St36
Control: DHMC pulmonary rehabilitation program

EA intervention will be applied sitting for 20 minutes prior to pulmonary rehab session.

Analysis

The blinded data will be submitted to Dartmouth Synergy Clinical and Translational Science Institute, Biostatistics Consultation core for independent statistical analysis.

Descriptive analysis of continuous variables will include median and interquartile range (IQR), or mean and standard deviation (SD) as appropriate. Categorical variables will be reported as counts and percentages. Baseline characteristics will be compared across all 3 groups using Chi-square test or Fisher's exact test where appropriate for categorical variables and t-test for continuous variables for all enrolled participants.

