Predictors of change in scores compared with baseline for outcomes each follow-up will be selected via stepwise general linear models with an inclusion criterion of $P < 0.1$ to enter and $P > 0.05$ to exit, while age and gender will be forced in the models. In addition, age, gender, and baseline outcomes will be included in all longitudinal outcome models. Outcomes analyses using changes from baseline at each follow-up, with a mixed-effects longitudinal regression model including a random individual effect to account for correlation between repeated measurements within individuals. Computations will be performed using SAS procedure PROC MIXED (SAS version 9.4, SAS Institute Inc., Cary, NC) or its equivalent. Statistical significance was defined as $p < 0.05$ based on a two-sided hypothesis test with no adjustments made for multiple comparisons.

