9.0 Study Timelines*

The study will use a wait-time control design with varying intervention durations, i.e., dose.

Group	T0	T1	T2	T3	T4	T5	T6	T7	T8	T9
A	ACU	ACU	ACU	ACU	ACU	ACU	ACU	ACU	T7 + 3MOS	T7 + 6MOS
B	WAIT CTRL	WAIT CTRL	WAIT CTRL	WAIT CTRL	ACU	ACU	ACU	ACU		
C	CTRL	CTRL	CTRL	CTRL	CTRL	CTRL	CTRL	CTRL		

T0 will be the project start time. T4 will be 4 weeks later. T8 will be 3 months after the completion of the intervention and T9 6 months after the completion of the intervention. Patients will be assessed at T0, T4, T8, and T9 for functional and quality of life.

Current practice at the DHMC pulmonary rehabilitation unit is 6 - 12 patient per rehab cohort. Their program is applied in 4- or 8- week increments.

As this is a pilot, part of the study's purpose is to evaluate the facilitators and barriers to recruitment. For example, this protocol can be extended in time if recruitment is slow. We will be aiming for at least 10 participants per arm. If recruitment is robust, we will cap each arm at 30 participants.

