10.0 Inclusion and Exclusion Criteria*

• Inclusion Criteria:

- Patients must be 21 y.o. of age or older and qualify to participate in the pulmonary rehab program at DHMC

• Exclusion Criteria:

- Severe cognitive impairment
- Active pulmonary exacerbation
- Unstable cardiopulmonary disease
- Actively receiving chemotherapy
- Adults unable to consent

PROTOCOL TITLE: Exploring the Dose-Response Effect of Adjunctive Acupuncture on Pulmonary Rehabilitation: A Pilot Study

- Pregnant women
- Prisoners

Patients who are randomized to groups A and B will be asked additional questions in preparation to receive acupuncture safely.

Patients will be randomized to one of two arms.

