14.0 Withdrawal of Subjects*

- If subjects might be withdrawn from the study if they engage in disruptive behavior as defined by DHMC. We would follow DHMC guidelines to terminate any relations with said patient.

PROTOCOL TITLE: Exploring the Dose-Response Effect of Adjunctive Acupuncture on Pulmonary Rehabilitation: A Pilot Study

- If subjects leave the study for any reason, their data will be censored from that point onward.

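### Exacerbation incidence has no analysis of its own and falls by default under a Gaussian change-from-baseline mixed model that does not suit it

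*Combined protocol and SAP*

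**What the plan says.** Section 4.0 (Study Endpoints) lists "The incidence of Acute Exacerbations (AE") alongside lung function, inflammatory markers, questionnaires and walking distance. It does not say what counts as an exacerbation, over what period events are counted, or whether the endpoint is a count, a rate or a yes/no.

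The analysis text in Section 6.0 is repeated in Section 17.0. Its one inferential outcome method reads: "Outcomes analyses using changes from baseline at each follow-up, with a mixed-effects longitudinal regression model including a random individual effect". On software it says "Computations will be performed using SAS procedure PROC MIXED", or an equivalent. On covariates it says "age, gender, and baseline outcomes will be included in all longitudinal outcome models", with no exception for any endpoint. Neither section mentions a count, rate, binary or time-to-event model, or an exposure term.

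Three other places bear on the point:

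- Section 9.0: "Patients will be assessed at T0, T4, T8, and T9 for functional and quality of life". T4 is week 4, and T8 and T9 fall 3 and 6 months after the intervention ends.
- Section 10.0 excludes patients with "Active pulmonary exacerbation" at entry. No exacerbation history before enrolment is planned.
- Section 14.0 says of people who leave that "their data will be censored from that point onward".

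**The concern.** An incidence is a number of events over a period of observation. The stated model treats every outcome as a roughly normal measurement with a value at T0 from which to compute a change. For exacerbations no such T0 value is defined. If current status at entry were used, the exclusion makes it zero for everyone: the change is then just the later count, and the required covariate is a constant.

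The windows between assessments differ about fourfold in length, so the variance of the count differs by visit. A model with only a random individual effect and one residual variance assumes that it does not. Censoring at withdrawal can make person-time differ between patients, and the model has no term for it.

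What is at stake is whether a by-visit p-value for exacerbations can be trusted, and whether arms with different observation time can be compared fairly.

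**Working it through.** The documents give no exacerbation rate, dropout rate, sample size derivation or power, so there is no stated figure to reproduce.

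**Inputs from the documents.** T0, T4, T8 and T9 assessments; at least 10 participants per arm, with a cap of 30 per arm also stated (Sections 6.0 and 9.0); two-sided 5% level.

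**Assumptions.** The intervention ends at week 8, and 3 months is 13 weeks. Events are counted within each window. Rates are 0.5 to 1.5 per patient-year. Overdispersion, where used, is gamma-mixed Poisson with mixing variance 1.

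**1. Windows.** T8 is week 8 + 13 = 21 and T9 is week 8 + 26 = 34. The windows are 4, 21 − 4 = 17 and 34 − 21 = 13 weeks, 34 in total.

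**2. Sparsity.** Expected events per patient are rate × 34/52, and the Poisson chance of none is exp(−that value).

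| Rate per year | Events per patient | Events per arm of 10 | Patients with none |
|---|---|---|---|
| 0.5 | 0.327 | 3.3 | 72% |
| 1.0 | 0.654 | 6.5 | 52% |
| 1.5 | 0.981 | 9.8 | 38% |

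**3. By-visit tests, by hand.** With no true effect, the Poisson variance of a window count is proportional to window length. A random-intercept model with one residual variance uses the average, (4 + 17 + 13)/3 = 11.33. The true-to-assumed variance ratio is r = length/11.33, and the actual two-sided error is 2 × [1 − Φ(1.96/√r)].

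| Visit | r | 1.96/√r | Type I error |
|---|---|---|---|
| T4 | 0.353 | 3.30 | 0.1% |
| T8 | 1.500 | 1.60 | 11.0% |
| T9 | 1.147 | 1.83 | 6.7% |

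For pure Poisson counts the rate cancels out of r. With overdispersion the variance is μ + μ². At 1 per year the means are 0.077, 0.327 and 0.250 and the variances 0.083, 0.434 and 0.312 (average 0.276). The ratio at T8 becomes 1.57 and the error about 11.8%.

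**4. By simulation.** There were 20,000 trials per setting, three arms of 10 or 30, no true effect, equal follow-up, zero baseline, and no age or gender terms. For overdispersed counts at 0.5 to 1.5 per year, the A versus C contrast rejected in 0.0% to 0.4% of trials at T4, 11% to 12% at T8 and 6% to 7% at T9. This agrees with the hand calculation. The overall contrast across visits rejected in 3.8% to 4.5% of trials at 10 per arm and 4.6% to 5.0% at 30 per arm.

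**5. What a replacement must handle.** With equal follow-up, overdispersed counts and 10 per arm, a plain Poisson exact test rejects a true null in 2.9%, 7.4% and 11.3% of trials at 0.5, 1 and 1.5 per year. An exposure term alone is therefore not enough. Poisson regression with robust errors and a log follow-up offset, with 25% of one arm leaving at T4, gave 1.2% to 8.5% across Poisson and overdispersed settings. With a small-sample t correction this became 0.3% to 4.7%.

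**6. Empty arms.** At 0.5 per year an arm of 10 has no events with probability exp(−3.27) = 0.038 under Poisson, or (1/1.327)^10 = 0.059 under overdispersion. The chance that at least one of two arms is empty is 1 − (1 − 0.038)² ≈ 7.5%, or 1 − (1 − 0.059)² ≈ 11.5%. With 25% of one arm leaving at T4, simulation gave 11% to 17%.

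**The case against.** The analysis text never names exacerbations. Section 6.0 also says "Categorical variables will be reported as counts and percentages", and an incidence could be reported that way. This stands in part: that the mixed model applies is a default reading. But the sentence is a general descriptive rule that supplies no denominator or window. Either the endpoint goes to the only model or it has no prespecified analysis, and the same edit cures both.

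The by-visit error rates depend on one variance being pooled over visits. A fit with a separate residual variance per visit would lessen the problem. The plan names only a random individual effect, so pooling is the plain reading, and analysis at each follow-up makes by-visit contrasts the natural output.

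A reader might go further in four ways that the documents do not support:

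- *That the exacerbation result must be wrong.* With equal follow-up the overall test roughly keeps its level.
- *That the model cannot be fitted.* A constant baseline merges with the intercept and drops out. That alone adds no bias.
- *That leavers would be scored as having few exacerbations, so that an arm with more dropout looks protected.* That describes raw totals from T0 to T9. In a model by follow-up, a leaver's later visits are missing, not zero. Simulated random dropout of 20% or 30% in one arm at T4 left the group estimate within about 1.5 standard errors of zero when a visit term was included. The plan names no visit term, and omitting it left a bias of about 3% to 16% of the mean interval count. No dropout rate is stated.
- *That only group A is followed to T8 and T9, because only its cells are filled in the Section 9.0 table.* The text does not limit those visits to A, and the blanks may come from table extraction.

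**Conclusion.** The concern holds in this form: a listed endpoint has no suitable prespecified analysis, and the model it would inherit does not fit an incidence. No baseline incidence is defined, the windows are unequal, and person-time is not used.

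The demonstrable error is in by-visit testing: under 1% at T4, about 11% to 12% at T8 and 6% to 7% at T9, against a nominal 5%. This rests on events counted per window, a pooled variance, equal follow-up and assumed rates of 0.5 to 1.5 per year. The pattern comes mainly from the window lengths and changes little with the rate. The size of any distortion from unequal exposure cannot be given, because the documents predict no difference in follow-up between arms.

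In an exploratory pilot with no power claim this is a moderate gap. It should be corrected, but it does not undermine the other endpoints.

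**What to change.** In Sections 6.0 and 17.0:

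- Exclude exacerbations from the change-from-baseline mixed model.
- Define the event for analysis purposes, and count events from T0 to T9 or last contact, whichever comes first.
- Report events and person-weeks per arm as the main result.
- Where events allow, add a rate ratio with its 95% confidence interval, labelled exploratory. Use a log follow-up offset and a model that allows for overdispersion: negative binomial, or Poisson with robust errors and a small-sample correction.
- State that if an arm has no events, only events and person-weeks are reported.

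The cost is a definition, a few sentences and one extra model. Event and last-contact dates must be recorded, and the documents do not say that they are. At 10 per arm the interval will be wide, and the ratio may be inestimable if an arm has no events.

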5.0 Study Intervention/Investigational Agent

Acupuncture is one of the oldest, most commonly used medical procedures in the world. Acupuncture is a method of encouraging the body to promote natural healing and to improve functioning through the application of needles and heat or other forms of energy such as electricity at specific points on the body. Electro acupuncture uses mA electricity at varying frequencies for its energy input.

There are 361 defined points in traditional acupuncture. Most are described by a combination of their affiliated organ, position on the traditional meridian and their set of functions. The points being used in the intervention are the Lung Mu-Shu points and St36 which are related to lung function and general function. The control group will undergo the standard pulmonary rehab program.

The EA will be applied just prior to the patients scheduled pulmonary rehab session. The EA generator will be placed on these points and amperage will be adjusted with feedback from the patient to just below the ability of the patient to sense the electricity. The ES intervention will be applied for 20 minutes.

All acupuncture needles are surgical grade steel, sterile, single use and disposable.

The EA unit is the ITO ES 130. It is compliant with FDA regulations (Approved by FDA 2008, re K081943). This device is currently in regular use treating patients in the DHMC GIM Acupuncture clinic.

This protocol does not deviate from standard of care options available to DH patients. DH patients will be receiving the highest standard of care in both pulmonary rehab and in acupuncture.

6.0 Procedures Involved*

The study will use a wait-time control design with varying intervention durations, i.e., dose.

Group	
A	INTERVENTION- 8 weeks acupuncture
B	INTERVENTION- 4 week acupuncture
C	SOC CONTROL- standard of care for the study duration

PROTOCOL TITLE: Exploring the Dose-Response Effect of Adjunctive Acupuncture on Pulmonary Rehabilitation: A Pilot Study

Patients will be recruited from the DHMC pulmonary rehab program. They will be randomized to start in group A or B with groups A and B to the EA intervention of 4 or 8 weeks or will volunteer to be a control subject in group C.

Current practice at the DHMC pulmonary rehabilitation unit is 6 - 12 patient per rehab cohort. Their program is applied in 4- or 8- week increments.

As this is a pilot, part of the study is to evaluate the facilitators and barriers to recruitment. For example, this protocol can be extended in time if recruitment is slow. We will be aiming for at least 10 participants per arm. If recruitment is robust, we will cap each arm at 30 participants.

Intervention: DHMC pulmonary rehabilitation program + EA Lung Mu-Shu+ St36
Control: DHMC pulmonary rehabilitation program

EA intervention will be applied sitting for 20 minutes prior to pulmonary rehab session.

Analysis

The blinded data will be submitted to Dartmouth Synergy Clinical and Translational Science Institute, Biostatistics Consultation core for independent statistical analysis.

Descriptive analysis of continuous variables will include median and interquartile range (IQR), or mean and standard deviation (SD) as appropriate. Categorical variables will be reported as counts and percentages. Baseline characteristics will be compared across all 3 groups using Chi-square test or Fisher's exact test where appropriate for categorical variables and t-test for continuous variables for all enrolled participants.

Predictors of change in scores compared with baseline for outcomes each follow-up will be selected via stepwise general linear models with an inclusion criterion of $P < 0.1$ to enter and $P > 0.05$ to exit, while age and gender will be forced in the models. In addition, age, gender, and baseline outcomes will be included in all longitudinal outcome models. Outcomes analyses using changes from baseline at each follow-up, with a mixed-effects longitudinal regression model including a random individual effect to account for correlation between repeated measurements within individuals. Computations will be performed using SAS procedure PROC MIXED (SAS version 9.4, SAS Institute Inc., Cary, NC) or its equivalent. Statistical significance was defined as $p < 0.05$ based on a two-sided hypothesis test with no adjustments made for multiple comparisons.

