13.0 Recruitment Methods

- Subjects will be recruited from the pulmonary rehabilitation clinic.
- Subjects will be identified and made aware of the study through their pulmonary providers.
- Flyers will be posted in the pulmonary rehabilitation clinical exam rooms to allow for self-referral for the control group as well as encourage conversation with their providers regarding participation in groups A and B.

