17.0 Data Management* and Confidentiality

The blinded data will be submitted to Dartmouth Synergy Clinical and Translational Science Institute, Biostatistics Consultation core for independent statistical analysis.

Descriptive analysis of continuous variables will include median and interquartile range (IQR), or mean and standard deviation (SD) as appropriate. Categorical variables will be reported as counts and percentages. Baseline characteristics will be compared across all 3 groups using Chi-square test or Fisher's exact test where

PROTOCOL TITLE: Exploring the Dose-Response Effect of Adjunctive Acupuncture on Pulmonary Rehabilitation: A Pilot Study

appropriate for categorical variables and t-test for continuous variables for all enrolled participants.

Predictors of change in scores compared with baseline for outcomes each follow-up will be selected via stepwise general linear models with an inclusion criterion of $P < 0.1$ to enter and $P > 0.05$ to exit, while age and gender will be forced in the models. In addition, age, gender, and baseline outcomes will be included in all longitudinal outcome models. Outcomes analyses using changes from baseline at each follow-up, with a mixed-effects longitudinal regression model including a random individual effect to account for correlation between repeated measurements within individuals. Computations will be performed using SAS procedure PROC MIXED (SAS version 9.4, SAS Institute Inc., Cary, NC) or its equivalent. Statistical significance was defined as $p < 0.05$ based on a two-sided hypothesis test with no adjustments made for multiple comparisons.

This is a pilot study so power analysis is not applicable.

All collected data will be anonymized and stored on password protected hard drives behind the hospitals firewall. Only the PI or his designee will be allowed access to the data. At the end of the study all key tables mapping identifiable data to unique identifiers will be erased. All data will be kept in compliance with DHMC data policies.

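### Group C is made up of volunteers and is the only group without EA by T8/T9, but the analysis neither names the randomised A-B contrasts nor sets comparisons with C apart as non-randomised

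*Combined protocol and SAP*

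**What the plan says.** **Allocation.** Section 6.0 randomises between A and B; otherwise a patient joins C by choice: "or will volunteer to be a control subject in group C". Section 10.0 agrees that only A and B are randomised: "Patients will be randomized to one of two arms". Section 13.0 adds that flyers are posted "to allow for self-referral for the control group", while patients for A and B are encouraged to talk to their providers.

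**Exposure.** Section 6.0 describes C as "SOC CONTROL- standard of care for the study duration". In the Section 9.0 table A has EA from T0 to T7, B waits from T0 to T3 and has EA from T4 to T7, and C has none. Section 9.0 also states: "Patients will be assessed at T0, T4, T8, and T9 for functional and quality of life". T8 and T9 fall 3 and 6 months after the intervention ends.

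**Analysis (Section 6.0, repeated in 17.0).** "Baseline characteristics will be compared across all 3 groups". The outcome model is given as "Outcomes analyses using changes from baseline at each follow-up, with a mixed-effects longitudinal regression model including a random individual effect". On covariates, "age, gender, and baseline outcomes will be included in all longitudinal outcome models", and further predictors are chosen stepwise. Significance is two-sided p<0.05 without multiplicity adjustment. The text does not say how group or dose enters the model, and it names no contrast.

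**Hypotheses (Section 2.0).** The objectives are worded as exploratory. The hypotheses below them predict significant effects of EA and a significant dose-response relationship.

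**The concern.** The trial contains two kinds of evidence. A v B is protected by randomisation. Anything against C is an observational comparison with people who chose not to have, or were not offered, EA. Nothing in the analysis text keeps the two apart.

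This matters most at T8 and T9. By then B has also had EA, so the only EA v no-EA comparison is with C, and C is the only zero-dose point on a dose-response curve. If C differs from A and B in prognosis, motivation or attitude to acupuncture, that difference would be read as an EA or dose effect. The randomised wait-control comparison, A v B at T4, is what the design's name points to, yet the analysis never mentions it.

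**Working it through.** The plan gives no power calculation, effect size or SD, so there is no stated figure to reproduce. The check has four parts.

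**1. What each comparison is, by visit (Sections 6.0 and 9.0)**

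| Visit | A v B (randomised) | A or B v C (not randomised) |
|---|---|---|
| T4 | 4 weeks of EA v none, if B is assessed before its first session | A: 4 weeks v none; B: none v none |
| T8, T9 | 8 v 4 weeks of EA; start time also differs (T0 v T4) | A: 8 weeks v none; B: 4 weeks v none |

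The T4 column is also B's first EA column, and the plan does not say which comes first, the assessment or the session.

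**2. How often selection alone gives p<0.05 against C**

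Inputs: 10 per group (Section 6.0 target; 30 in total in Sections 1.0 and 12.0), two-sided 0.05. Assumptions not in the documents: no EA effect, and a gap d between C and an EA group of 0.3, 0.5 or 0.8 SD.

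(a) *The gap survives adjustment.* Two-sample t-test, df = 18, critical value 2.101, noncentrality d / √(1/10 + 1/10):
- d = 0.3: noncentrality 0.671, rejection 9.7%
- d = 0.5: 1.118, 18.5%
- d = 0.8: 1.789, 39.5%

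(b) *The gap is equally present in the baseline outcome, which is adjusted for.* Simulated ANCOVA, 10 v 10, baseline/follow-up correlation r (assumed):
- r = 0.5: 6.4%, 8.9%, 14.2%
- r = 0.8: 5.5%, 6.3%, 8.0%
- mean of T8 and T9, with age and gender also in the model: 6.5%, 9.2%, 15.4% (r = 0.5) and 5.6%, 6.1%, 8.4% (r = 0.8)

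(c) *Would the planned baseline comparison show the gap?* For one characteristic and one pair of groups the detection rate is the same as in (a). A true 0.5 SD gap is therefore missed in 1 − 0.185 = 0.815, about 81% of trials.

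With no EA effect, the randomised A-B test stays at its nominal 5%.

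**3. Dose-response**

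Take a linear 0/4/8-week term at one time point, equal groups, unadjusted. The centred doses for C, B and A are −4, 0 and +4, so the slope is 4(A − C) / (16 + 0 + 16) = (A − C)/8. B's mean has weight zero, and the randomised A-B difference plays no part.

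This is a special case. Suppose instead that cumulative dose is a time-varying linear term over T4, T8 and T9 with time effects (an assumption). At T4 the doses for A, B and C are 4, 0 and 0, centred at 8/3, −4/3 and −4/3; at T8 and T9 they are centred at 4, 0 and −4. With zero within-person correlation the denominator is 96/9 + 32 + 32 = 74.67, so B's T4 mean has weight −1.333/74.67 = −0.018. At correlation 0.7 B's weights are −0.061 at T4 and +0.025 at each of T8 and T9, and the summed weight on C falls in size from −0.125 to −0.075. Unequal groups also bring B in: with 20 in C and 10 each in A and B, B's single-time weight is 0.023.

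**4. Precision of the randomised contrast**

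At 10 v 10 the unadjusted 95% CI half-width is 2.101 × √(2/10) = 0.94 SD. With baseline adjustment (simulated) it is about 0.83 SD at r = 0.5 and 0.57 SD at r = 0.8.

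**The case against.** The other side has real weight. This is a pilot with exploratory objectives, and evaluating recruitment is one of its stated purposes. How C is formed is disclosed in Sections 6.0, 10.0 and 13.0. All three groups come from one rehabilitation programme under the same eligibility criteria, which narrows the room for selection. The model adjusts for age, gender and baseline outcome, and baseline is compared across the groups. All of this stands and lowers the risk. It does not answer the point, because the same plan sets a significance threshold and predicts significant effects without saying which comparison may carry that claim.

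Three stronger readings are tempting, and the documents do not support them.
- *The plan tests EA against volunteers.* No outcome comparison with C is written down. The plan permits it; it does not specify it.
- *The dose-response estimate ignores the randomised difference.* That is exact only for the single-time, unadjusted, equal-group trend. The plan has a longitudinal model with T4 among its visits, and Section 6.0 allows 10 to 30 per arm, so B may well contribute.
- *The error rate lies between about 5% and 40%.* Those figures follow from assumed gaps and correlations. They are not limits for this trial.

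**Conclusion.** The point holds as a gap in the analysis text. Randomised and non-randomised comparisons are not distinguished, so the Section 2.0 hypotheses could be declared supported on a comparison with self-selected patients. The allocation, exposure and analysis facts come straight from the documents. The size does not: the rates of 10%, 19% and 40%, or about 5-15% when the baseline outcome captures the gap, show only that gaps too small for the baseline comparison to detect reliably can matter. The direction of any selection is also unknown. The remedy is a cheap improvement. It makes clear what the trial can conclude without adding patients or an arm.

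**What to change.** In Sections 6.0 and 17.0:

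1. State that the randomised contrasts are A v B at T4 (EA v wait control, with B assessed before its first EA session) and A v B at T8 and T9 (8 v 4 weeks of EA, noting that start time also differs), and that randomised evidence on EA and on dose comes from these.
2. State that every comparison with C, and any 0/4/8-week trend that includes C, is non-randomised, is reported as a covariate-adjusted estimate with a 95% confidence interval, and is not presented as confirming the EA or dose-response hypothesis.

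In Section 9.0, confirm that B is assessed at T8 and T9. The extracted table fills those cells for A only. The text implies that all patients are assessed, so the blanks may come from the PDF reading.

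**Cost.** Wording, plus one scheduling rule for B at T4; it should be settled before outcomes are examined by group. The A-B contrast has limits that should be stated with it. It is imprecise at 10 v 10 (half-widths above). No sham or patient masking is described, so it is open-label. At T4 it covers only 4 weeks of EA. It may not reach the inflammatory-marker hypothesis, because Section 9.0 lists only functional and quality-of-life assessments.
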